8.4.3. Reporting Unanticipated Problems to Subjects

Subjects will be informed of any UPs that occur as part of their participation in this study.

9. STATISTICS

9.1. Statistical analysis

Analysis of the primary endpoint

The primary efficacy outcome for the first part of the study is ‘Clinical status of the patient (according to 7-point ordinal scale) on day 15 as compared to baseline’.

Analysis of the secondary endpoints

The interval (quantitative) data will be described with arithmetic mean, standard deviation, median, lower quartile (25%) and higher quartile (75%), minimum, maximum, coefficient of variation, and 95% confidence interval for the mean. The categorical (qualitative) data will be described with incidences, percentage, or proportions, and 95% confidence interval for percentage or proportions.

The time to event data will be processed via survival analysis with the use of Kaplan-Meier curves and 95% confidence intervals.

The following standard parametric tests are planned for comparison of quantitative data with normal distribution: Student t-test, analysis of variance (ANOVA) for repeated measurements.

The following standard non-parametric tests are planned for comparison of quantitative data with distribution other than normal: Mann-Whitney U-test, Wilcoxon T-test, Friedman test.

Shapiro-Wilk test will be used to test normality of the distribution.

The incidences will be compared with Pearson’s χ^2 -test or Fischer’s exact test.

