Open multi-centre observational study of efficacy and safety of a medicinal

	
product.
 
The clinical efficacy will be assessed by changes in the patient's clinical status, duration of hospitalization, oxygenation/mechanical ventilation. The clinical examination will include clinical, laboratory, and instrumental investigations according to the current guidelines on treatment of COVID-19 in the Russian Federation.

POPULATION	Hospitalized patients of 18 years and older with confirmed COVID-19.
SAMPLE SIZE	At least 50 patients
TREATMENT ALLOCATION	All study subjects will receive treatment with Polyoxidonium, lyophilizate, 12 mg, in addition to the standard treatment
DIAGNOSIS	Verified COVID-19

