4. STUDY DESIGN

4.1. Primary and Secondary Outcomes

According to the aim and objectives of this study, safety and efficacy of Polyoxidonium®, lyophilizate for solution for injections and topical application, 6 mg (NPO Petrovax Pharm LLC, Russia) will be evaluated in hospitalized patients with coronavirus disease (COVID-19).

Efficacy outcomes

Primary efficacy outcome

Subject clinical status using the WHO 7-point ordinal scale on day 15 as compared to baseline.

1. Not hospitalized, no limitations on activities.
2. Not hospitalized, limitation on activities.
3. Hospitalized, not requiring supplemental oxygen.
4. Hospitalized, requiring supplemental oxygen.
5. Hospitalized, on non-invasive ventilation or high flow oxygen devices.
6. Hospitalized, on invasive mechanical ventilation or ECMO.
7. Death.

Secondary efficacy outcomes

Clinical severity assessed by scales

1. Subject clinical status using the WHO 7-point ordinal scale

- Time to improvement of each parameter of the primary scale from admission.

- Subject clinical status at days 3, 5, 8, 11, and 29.
 - Average change in the clinical status at days 3, 5, 8, 11, 15, and 29 as compared to baseline.
2. *The NEWS Score (National Early Warning Score) describes the vital signs (pulse rate, breathing rate, temperature, blood pressure etc.) and its deviation from the reference ranges):* is evaluated daily and on day 15.
- The time to discharge or to a NEWS of ≤ 2 and maintained for 24 hours, whichever occurs first.
 - Change from baseline to days 3, 5, 8, 11, 15, and 29 in NEWS.
3. *Oxygenation, including mechanical ventilation:*
- Change (day by day) in the need for oxygenation in the first 28 days (up to day 29).
4. *Hospitalization*
- Duration of hospitalization (days).
5. *Mortality (date, cause)*
- 28-day mortality.
6. *SOFA scale (evaluation of organ failure associated with sepsis):* is evaluated daily and on day 15.
- Change from baseline to days 3, 5, 8, 11, 15, and 29 in SOFA.

Safety outcomes

Safety outcomes

- Cumulative incidence of serious adverse events/reactions (SAEs, SARs)
- Cumulative incidence of adverse events/reaction (AEs, ARs)
- Permanent or temporary discontinuation of infusions/injections (by any cause)
- Clinically significant changes in the levels of leukocytes, haemoglobin, platelets, creatinine, glucose, total bilirubin, ALT, AST, CRP, and other parameters.

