Patients who meet the inclusion criteria and do not meet any of the exclusion criteria will be included in a single study group, that will receive Polyoxidonium®, lyophilizate for solution for injections and topical application, 6 mg (NPO Petrovax Pharm LLC, Russia) in dose of 12 mg once daily intravenously (IV) for 3 days, then every other day intramuscularly (IM) on days 5–17 (the total treatment course is 10 injections).

The data collected in this observational program should help doctors find more effective therapy for other patients with COVID-19.

The study will include the following periods:

- **Treatment period** (17 days in total, days 1...17, if the study criteria are met) with administration of the investigational product (IP) (intravenous injections for 3 days, then intramuscular injections for 14 days), assessment of the clinical status, recording of AEs.

- **Follow-up period** (days 18...29±3)

Figure 4.1 shows the study flow chart.

[figure not shown]

Figure 4.1. Study flow chart

¹ MASTER PROTOCOL. A Multi-centre, Adaptive, Randomized, Double-Blind, Placebo-Controlled Clinical Trial of the Safety and Efficacy of Investigational Therapeutics for the Treatment of COVID-19 in Hospitalized Patients. Electronic source Free access: <https://www.who.int/blueprint/priority-diseases/key-action/multicenter-adaptive-RCT-of-investigational-therapeutics-for-COVID-19.pdf>. Access date: March 13, 2020

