7. ASSESSMENT OF EFFICACY AND PHARMACODYNAMIC EFFECTS

7.1. Efficacy outcomes

According to WHO Master Protocol, the primary endpoint will be evaluated on day 15 of the first part of the study. The day of the primary endpoint may be modified based on a blinded evaluation of various days because there is uncertainty about the clinical course and potential different trajectories according to baseline disease severity¹.

Efficacy outcomes

Primary efficacy outcome

Subject clinical status using the WHO 7-point ordinal scale on day 15 as compared to baseline.

6. Not hospitalized, no limitations on activities.
7. Not hospitalized, limitation on activities.
8. Hospitalized, not requiring supplemental oxygen.
9. Hospitalized, requiring supplemental oxygen.
10. Hospitalized, on non-invasive ventilation or high flow oxygen devices.
11. Hospitalized, on invasive mechanical ventilation or ECMO.
12. Death.

Secondary efficacy outcomes

Clinical severity assessed on scales

1. Subject clinical status using the WHO 7-point ordinal scale

- Time to improvement of each parameter of the primary scale from admission.
- Subject clinical status at days 3, 5, 8, 11, and 29.
- Average change in the clinical status at days 3, 5, 8, 11, 15, and 29 as compared to baseline.

2. The NEWS Score (National Early Warning Score) describes the vital signs (pulse rate, breathing rate, temperature, blood pressure etc.) and its deviation from the reference ranges): is evaluated daily and on day 15.

- The time to discharge or to a NEWS of ≤ 2 and maintained for 24 hours, whichever occurs first.
- Change from baseline to days 3, 5, 8, 11, 15, and 29 in NEWS.

3. Oxygenation, including mechanical ventilation:

- Change (day by day) in the need for oxygenation in the first 28 days (up to day 29).

4. Hospitalization

- Duration of hospitalization (days).

5. Mortality (date, cause)

- 28-day mortality.

6. SOFA scale (evaluation of organ failure associated with sepsis): is evaluated daily and on day 15.

- Change from baseline to days 3, 5, 8, 11, 15, and 29 in SOFA.

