9.7.2.2. Analysis of the secondary efficacy endpoints

The interval (quantitative) data will be described with arithmetic mean, standard deviation, median, lower quartile (25%) and higher quartile (75%), minimum, maximum, coefficient of variation, and 95% confidence interval for the mean. The categorical (qualitative) data will be described with incidences, percentage, or proportions, and 95% confidence interval for percentage or proportions.

The time to event data will be processed via survival analysis with the use of Kaplan-Meier curves and 95% confidence intervals.

The following standard parametric tests are planned for comparison of quantitative data with normal distribution: Student t-test for dependent/independent samples, analysis of variance (ANOVA) for repeated measurements.

The following standard non-parametric tests are planned for comparison of quantitative data with distribution other than normal: Mann-Whitney U-test, Wilcoxon T-test, Friedman test.

Shapiro-Wilk test will be used to test normality of the distribution.

The incidences will be compared between the treatment groups with Pearson's χ^2 -test or Fischer's exact test.

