9.8. Level of significance

The significance level will be 0.05 (5%).

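### No valid named test for within-patient changes in proportions: the plan names only Pearson and Fisher, and 9.7.2.2 ties them to treatment groups that do not exist

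*Combined protocol and SAP*

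**What the plan says.** Section 4.2 states that eligible patients "will be included in a single study group". The synopsis sets the sample size at "At least 50 patients", and section 9.8 sets the significance level at 0.05 without stating sidedness.

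For proportions, section 9.1 says "The incidences will be compared with Pearson" (chi-square) or Fisher's exact test, and the synopsis repeats this. Section 9.7.2.2 is more specific: "The incidences will be compared between the treatment groups with Pearson" or Fisher. No section names McNemar's test, Cochran's Q, a GEE or a mixed logistic model.

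For quantitative data the list does include within-patient methods. Section 9.1 gives repeated-measures ANOVA and "Mann-Whitney U-test, Wilcoxon T-test, Friedman test", of which the last two are paired or repeated-measures tests. Section 9.7.2.2 adds the t-test for dependent samples.

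One secondary outcome in section 4.1 is binary and repeated within patients: "Change (day by day) in the need for oxygenation in the first 28 days (up to day 29"). It stands under oxygenation, including mechanical ventilation.

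The only intervals planned for categorical data (synopsis, 9.1, 9.7.1, 9.7.2.2) are 95% intervals for a percentage or proportion.

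**The concern.** With a single group, any change over time in the share of patients on oxygen or ventilation compares the same patients with themselves. Pearson and Fisher compare the two totals as though they came from different people and ignore who changed. The plan recognises pairing for quantitative data but offers nothing for binary data, and the comparison it does describe has no second group.

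Deleting the reference to treatment groups would not be enough, because the named tests would still assume independent samples. An analyst would then have to use an unsuitable test or choose one after seeing the data. At about 50 patients that choice can move a result across the 0.05 line.

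**Working it through.** **Inputs from the documents.** n = 50 (synopsis, a minimum); alpha = 0.05 (9.8), taken as two-sided; one group (4.2). The plan gives no figure to reproduce: no power, effect size, rates or within-patient correlation.

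**Assumed inputs.** Proportions 50% and 50% (no change), 50% to 30%, and 60% to 45%; correlation φ between the two binary readings from -0.2 to 0.6; all 50 pairs complete.

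**Step 1: large-sample size.** With equal proportions p at both times, the true variance of the difference is 2p(1-p)(1-φ)/n. Pearson assumes 2p(1-p)/n. The true size of a nominal 5% Pearson test is therefore 2[1 - Φ(1.96/√(1-φ))].
- φ = 0.2: 1.96/0.894 = 2.19, size 2.8%.
- φ = 0.6: 1.96/0.632 = 3.10, size 0.2%.
- φ = -0.2: 1.96/1.095 = 1.79, size 7.4%.

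**Step 2: size and power at n = 50.** These come from 400,000 simulated sets of 50 pairs per row, with P(both) = p1·p2 + φ√[p1(1-p1)p2(1-p2)]. With b patients changing one way and c the other, asymptotic McNemar is (b-c)²/(b+c) on 1 df. Exact McNemar is the two-sided binomial test of b against c; mid-p subtracts the probability of the observed split from the exact p-value (when b and c differ). Pearson is uncorrected.

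True size, 50% at both times:

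| φ | Pearson | Fisher | McNemar, asymptotic | McNemar, mid-p | McNemar, exact |
|---|---|---|---|---|---|
| -0.2 | 8.3% | 5.5% | 5.2% | 4.5% | 3.0% |
| 0 | 5.7% | 3.5% | 5.3% | 4.4% | 2.9% |
| 0.2 | 3.4% | 1.9% | 5.3% | 4.6% | 3.0% |
| 0.3 | 2.3% | 1.2% | 5.1% | 4.7% | 3.0% |
| 0.5 | 0.7% | 0.3% | 4.4% | 4.4% | 2.5% |
| 0.6 | 0.3% | 0.1% | 4.3% | 4.2% | 2.2% |

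Power, 50% to 30%:

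| φ | Pearson | McNemar, asymptotic | McNemar, mid-p | McNemar, exact |
|---|---|---|---|---|
| 0.2 | 55% | 63% | 61% | 54% |
| 0.3 | 55% | 69% | 67% | 60% |
| 0.5 | 56% | 83% | 83% | 76% |
| 0.6 | 56% | 93% | 93% | 88% |

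Power, 60% to 45%:

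| φ | Pearson | McNemar, asymptotic | McNemar, mid-p | McNemar, exact |
|---|---|---|---|---|
| 0.1 | 34% | 36% | 33% | 27% |
| 0.3 | 31% | 43% | 42% | 34% |
| 0.6 | 26% | 65% | 65% | 55% |

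The exact test is conservative at this sample size and can fall below Pearson when φ is low.

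**Step 3: same totals, different pairs.** Take 25/50 at baseline and 15/50 later. Pearson gives p = 0.041 and Fisher 0.066 whatever the individual patients did.
- 10 improve, 0 worsen: asymptotic McNemar p = 0.0016, exact 0.002.
- 12 and 2: 0.0075, exact 0.013.
- 15 and 5: 0.025, exact 0.041.

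**Step 4: an example that crosses 0.05.** Take 30/50 falling to 22/50, with 9 improved and 1 worsened. Then 21 patients are on oxygen both times, so φ = (0.42 - 0.60×0.44)/√(0.60×0.40×0.44×0.56) = 0.64. Pearson p = 0.109 and Fisher 0.161. Asymptotic McNemar is (9-1)²/10 = 6.4, p = 0.011; exact p = 0.021. This example sits at the high end of the assumed correlation.

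**Step 5: intervals.** A single proportion at p = 0.5 has half-width 1.96√(0.25/50) = 13.9 points, and pairing does not enter. An interval for the change would be affected (18.8 points unpaired in Step 3, against 11.1, 13.6 or 16.6 paired), but the plan does not specify one.

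**The case against.** The strongest defence is that no section assigns Pearson or Fisher to a comparison of a later day with baseline. Section 9.7.2.2 points them at different patients, and the plan has comparisons where they are valid: baseline severity (9.7.2.1) and region, symptom duration, age and sex (9.9). Mortality and cumulative adverse-event incidence give one value per patient and raise no pairing issue. Sections 9.3 and 9.7 also let methods be replaced or added. All of this stands, so the numerical consequences are conditional on a use the plan does not state. It does not fill the gap: a stated within-patient outcome has no suitable method, and permission to choose one after data collection is not prespecification.

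A reader might infer more than the documents support:
- **That the planned error bars are wrong.** Only single-proportion intervals are planned, and these are sound in this respect.
- **That the WHO score is caught too.** "Subject clinical status using the WHO 7-point ordinal scale on day 15 as compared to baseline" is ordinal, and paired rank tests are on the list. That no test is assigned to it is a separate matter.
- **That 50 patients over 29 days would be counted as 50 × 29 = 1,450 independent people.** No section proposes such pooling.

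The impact is also limited. Under positive correlation the error is lost power, not false positives. In an uncontrolled cohort a sharper before-after p-value still cannot separate a drug effect from natural recovery.

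**Conclusion.** The gap is real and modest. The named tests for proportions do not fit the only over-time comparison a single-group study can make, and the comparison that 9.7.2.2 describes cannot be made between treatment arms. The size depends on assumed rates and correlation. For φ of 0.2 to 0.6 at n = 50, Pearson would run at about 3.4% down to 0.3% instead of 5%, and would give up roughly 8 to 37 points of power against asymptotic McNemar for a 50% to 30% change (63 - 55; 93 - 56). Near zero correlation the tests differ little; at -0.2 Pearson rejects about 8.3% of the time. The documents support the conclusion that a method is missing, not that any planned p-value or interval is already wrong.

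**What to change.** In the synopsis, 9.1 and 9.7.2.2:
- Delete the reference to treatment groups in 9.7.2.2.
- For a binary outcome at two time points, prespecify McNemar's test, asymptotic or mid-p, with a paired 95% confidence interval for the change. Avoid the exact version as the default because it is conservative at n = 50.
- For the daily oxygen and ventilation series, prespecify a logistic GEE clustered on patient, or Cochran's Q. Cochran's Q needs a value for every patient on every day analysed. Because 9.4 substitutes no missing data, the GEE is the easier of the two to apply.
- State that Pearson and Fisher are kept for comparisons between different patients, such as baseline severity and the 9.9 subgroups.

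The cost is SAP wording. No new data, visits or patients are needed.

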9.2. Software for statistical analysis

Statistical analysis of the data collected during the study will be performed with the use of programming language R for statistical computing (version 3.6.0 or higher), statistical software SAS (version 9.4 or higher) or other special software that ensures adequate quality of the results.

9.3. Review of violations from the protocol and plan of analysis

Statistical methods could be replaced if it contributes to a more correct and informative analysis. Any changes will be described and justified in the final study report.

9.4. Drop-outs, withdrawn patients, and missing data

No missing data will be substituted. The missing/omitted data will not be considered during statistical analysis.

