Visits to the clinic are preferred after discharge, but the quarantine or other reasonable factors can limit this opportunity. The visits could be performed in a form of phone call or with other remote communication technologies. Some data will not be collected by obvious reasons.

- Evaluation of the measures of clinical support.
- Assessment of the clinical status according to the 7-point ordinal scale — every day during hospitalization up to and including Day 17.
- Assessment of the clinical status according to the NEWS scale and SOFA scale.
- Oropharyngeal/nasal (OP/N) sample.
- Haematology.
- Blood chemistry.
- Urinalysis.
- Administration of the investigational product.
- Physical examination (including lung auscultation).
- Collection of the efficacy data (oxygenation, mechanical ventilation, prolongation of hospitalization).
- Collection of information about concomitant treatments.
- Recording of AEs.

Follow-up period

(Day 29±3)

Full list of the procedures is provided in Appendix 1.

The visits are performed in the in-patient settings. If the patient is discharged earlier, the procedures will be performed within the outpatient visits to the clinic (if possible).

- Evaluation of the measures of clinical support — only if the hospitalization is prolonged.
- Assessment of the clinical status according to the 7-point ordinal scale.
- Assessment of the clinical status according to the NEWS scale and SOFA scale.
- Oropharyngeal/nasal (OP/N) sample.
- Haematology.
- Blood chemistry.
- Urinalysis.
- Collection of the efficacy data (oxygenation, mechanical ventilation, prolongation of hospitalization).
- Collection of information about concomitant treatments.
- Physical examination (including lung auscultation).
- Recording of AEs.

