9.7.2. Statistical methods for efficacy analysis

ITT will be the main population for efficacy analysis.

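### The plan has no Day 15 WHO category for patients discharged alive and not reached; Sections 9.4 and 11.8 drop them, although ITT is the main efficacy population

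*Combined protocol and SAP*

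**What the plan says.** Section 4.1 defines the primary outcome: "Subject clinical status using the WHO 7-point ordinal scale on day 15 as compared to baseline". Categories 1 and 2 of the scale are the two non-hospitalized states, 3 to 6 are hospital states and 7 is death. Section 9.6 defines ITT as all enrolled patients, and Section 9.7.2 states: "ITT will be the main population for efficacy analysis". The synopsis sets the sample size: "At least 50 patients".

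On collecting the score, Section 6.2 (Days 2 to 18) lists: "Assessment of the clinical status according to the 7-point ordinal scale — every day during hospitalization up to and including Day 17". The same section moves procedures to outpatient visits when discharge comes before Day 17 and allows telephone or other remote contact. Table 1 marks the WHO scale in a daily column that ends at discharge and, separately, in the Day 15±1 column. Section 6.2 then concedes: "Visits to the clinic are preferred after discharge, but the quarantine or other reasonable factors can limit this opportunity". It adds that part of the data will not be obtained, without saying which items.

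On missing values, Section 9.4 states: "No missing data will be substituted. The missing/omitted data will not be considered during statistical analysis". Section 11.8 gives a missed visit as an example of a significant deviation and removes patients with significant deviations from the final efficacy analysis.

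**The concern.** A discharged patient with no Day 15 contact has no Day 15 value and leaves the primary analysis. The cause of the loss is linked to the outcome. Inpatients are scored daily and deaths take category 7, so the values most exposed to loss are those of patients well enough to go home. What remains describes patients who are in hospital, dead, or discharged and reached. That is not the all-enrolled question the plan sets itself.

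The loss would probably be uneven. Section 9.7.2.1 expects rapid recovery in mild disease and splits the analysis by baseline severity, so early discharge, and with it this loss, may concentrate in the mild-moderate stratum. It would also vary with how diligently each centre telephones. The plan already collects useful information on these patients: duration of hospitalization and 28-day mortality are secondary outcomes, and there is a Day 29 contact. Section 9.4 makes no use of it for the Day 15 category.

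**Working it through.** **Where the rules lead.** For a patient discharged on, say, Day 10 and not reached around Day 15:

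- Sections 6.2 and Table 1: a score is due, but none is obtained.
- Section 9.4: no value is substituted and the gap is ignored.
- Section 11.8: the missed visit is itself a ground for exclusion from the efficacy analysis.
- Sections 9.6 and 9.7.2: the patient belongs to the main efficacy population.
- Section 9.10: missing data are queried and reported, and sensitivity to uncorrectable errors is examined, but no category is assigned.
- Section 9.3: methods may be replaced, but this is not a pre-specified rule.

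**Size.** The plan has no figure to reproduce here; it gives no discharge rate, contact rate or sample-size derivation. The inputs are therefore assumptions, apart from N = 50:

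- d = share discharged alive before Day 15: 50%, 60%, 70%
- m = share of those not reached: 10%, 20%, 30%
- all discharged patients, reached or not, are still at home on Day 15 (relaxed below)

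True share in hospital or dead = 1 − d. Reported share = (1 − d)/(1 − d·m).

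| d | True | m = 10% | m = 20% | m = 30% |
|---|---|---|---|---|
| 50% | 50.0% | 52.6% (+2.6) | 55.6% (+5.6) | 58.8% (+8.8) |
| 60% | 40.0% | 42.6% (+2.6) | 45.5% (+5.5) | 48.8% (+8.8) |
| 70% | 30.0% | 32.3% (+2.3) | 34.9% (+4.9) | 38.0% (+8.0) |

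The relative error is d·m/(1 − d·m), from 0.05/0.95 = 5.3% to 0.21/0.79 = 26.6%.

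Middle case in patients: 30 of 50 discharged and 6 of those not reached, so 44 are analysed. Reported: 20/44 = 45.5%. True: 20/50 = 40%.

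A wider grid (40-80% discharged, 10-50% not reached) lowers the share in categories 1-2 by about 2 to 17 points and leaves 48 down to 30 patients analysed.

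**If some unreached patients are not at home.** Let r be the share of them readmitted or dead on Day 15. The true share becomes (1 − d) + d·m·r, which equals the reported share when r = (1 − d)/(1 − d·m). In the middle case that is 45.5%. With 2 of the 6 readmitted or dead, the truth is 22/50 = 44%, still below the reported 45.5%. With 3 of the 6, it is 23/50 = 46% and the error changes sign.

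**Bounds in the middle case.** Share in categories 1-2:

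- unreached patients all at home: 30/50 = 60%
- observed cases only: 24/44 = 54.5%
- unreached patients all readmitted or dead: 24/50 = 48%

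Scoring the six as category 1 rather than 2 moves the mean by 6/50 = 0.12 category.

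**The case against.** Two stronger readings are tempting, and the documents support neither.

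- **Scoring stops at discharge, so categories 1 and 2 would be empty on Day 15.** The line in Section 6.2 limits only the daily score. The same section continues procedures at outpatient visits or by telephone, and Table 1 has a separate Day 15±1 column. Section 6.2 and Table 1 can be read together; the gap concerns only patients who are not reached.
- **The missing category is known to be 1 or 2.** Discharge fixes the status on that date. An unreached patient may since have been readmitted (3 to 6) or died (7), and telling 1 from 2 needs information on activity.

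The best case for the plan is that few patients would be lost. Table 1 lists dosing on Days 15 and 17, there is a ±1 day window, Section 5.7.2 provides visit reminders, Section 4.5 requires documented attempts to contact patients lost to follow-up, and Section 9.10 has monitors look for missing data. The accepted data loss may mean swabs and blood tests rather than whether someone is at home. This argues for the lower end of the range. It does not supply a rule for those who are missed.

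It is also fair that the calculation concerns the Day 15 distribution, whereas Section 4.1 compares with baseline. A mild-moderate patient may start at category 3 and can then gain at most two categories, and dropping the patient removes the baseline value too. The error in change from baseline could be smaller or differ in sign. That part stands.

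Finally, assigning category 2 to patients of unverified status in an open single-arm study could favour the product. This also stands, and is why an unfavourable-case analysis must accompany the rule.

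**Conclusion.** The point holds in this form. A Day 15 score is planned for discharged patients, but those not reached have no assigned category and leave the primary analysis under Section 9.4, with Section 11.8 as a second route out. Both conflict with ITT as the main efficacy population.

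If these patients remain at home, the share in hospital or dead on Day 15 is overstated by 2.3 to 8.8 points, on assumed rates of 50-70% discharged and 10-30% of those not reached. If a substantial part were readmitted or died (about 45% in the middle case), the direction reverses. No direction is established for change from baseline.

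For scale, the 95% half-width for a proportion near one half with 50 patients is 1.96 × √(0.25/50) = 13.9 points. The illustrated error is smaller than that, but more patients would not reduce it. The change should be made; it does not make the study uninterpretable.

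**What to change.** 1. **Section 6.2.** Keep daily scoring "every day during hospitalization up to and including Day 17", and add that after discharge the Day 15 WHO status is obtained by telephone if needed. The contact should cover activity limitation, readmission and vital status, in line with the Day 15±1 column of Table 1.
2. **Section 9.4.** Except the WHO scale. A patient discharged alive before the scoring day, with no contact and no known readmission or death (including from later contact such as Day 29), is assigned category 2 in the primary ITT analysis.
3. **Sensitivity analyses.** Category 1 for all such patients; observed cases only; and an unfavourable case using the baseline category or death.
4. **Section 11.8.** Reconcile with Sections 9.6 and 9.7.2, so that a missed visit does not remove a patient from the primary analysis.

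The cost is a few sentences and the extra tables; no visits are added. The assigned category may be wrong for individual patients, and the sensitivity analyses bound the effect in both directions.
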